5.3.7. PARAMETERS OF SPECIAL INTEREST

Venous blood for determination of following parameters will be drawn during the clamp investigation as well as one day and one week after the clamp. Time points of sampling collection during the clamp are indicated in Figure 1.

Platelet activity parameters (PAP):

PAP are determined in the course of blood sampling at visits 2, 3, 4 and 5. In both Clamp tests, PAP are determined at five time points. The sodium citrate blood samples will be kept at ambient temperature after collection and transferred immediately to the Central Laboratory of the University

 endocrinology diabetology	Title: DIAPLATE-STUDY	Protocol No: Version 3.5	Sponsor: Medical University of Graz	Date: 13th February 2018
---	--------------------------	-----------------------------	--	-----------------------------

Hospital Graz for analyses. Detailed information about sampling will be summarized in the dedicated SOP.

Light transmission aggregometry

Measured on a Chronolog 700 Lumi-Aggregometer (Chronolog Corp, Havertown, PA) using standard agonists of platelet aggregation (Collagen, ADP, arachidonic acid, TRAP) to stimulate platelet aggregation in platelet-rich plasma (Gurbel PA et al. Circulation 2009)

Platelet Function Analyser-200

Measured on a PFA-200 (Siemens Healthineers, Marburg) using Collagen/ADP and Collagen/Epinephrine cartridges to monitor closure-time in-vitro.

Quantification of platelet function and activation by flow cytometry (FACS)

Blood samples will be processed for multicolour FACS analysis within 60min of collection. Fluorochrome-conjugated monoclonal antibodies will be used to stain platelet surface antigens, such as CD41 (platelet integrin $\alpha IIb\beta 3$), CD42b (platelet glycoprotein Ib), CD62P (platelet α -granule membrane protein), CD63 (platelet dense granule and lysosomal membrane protein) and PAC-1 (activation induced neoepitope on integrin $\alpha IIb\beta 3$). Single platelets will be identified according to the size and granularity parameters and the expression of CD41 and CD42b. Platelet activation markers (CD62P, CD63 and binding of PAC-1) will be quantified within $CD41^{pos}$ and $CD42b^{pos}$ platelets as well as $CD45^{pos}CD42b^{pos}$ platelet-leukocyte complexes using a BD LSRFortessa flow cytometer (Becton Dickinson, US).

Additional parameters:

- Interleukin-6 (IL6): IL 6 is a proinflammatory cytokine which is produced during acute inflammation and stimulates secretion of hepatic acute-phase-proteins[10, 11]. Higher serum levels of IL6 showed to be a risk factor for cardiovascular disease with and without diabetes mellitus[12-14]. Measurement is conducted by electroluminescence immunoassay (ECLIA)
- Von Willebrand factor (vWF): vWF is an essential glycoprotein initiating adhesion of thrombocytes to impaired endothelial wall. Especially in DM2 vWF showed to be associated with risk of cardiovascular disease [15, 16]. We will measure vWF concentrations by ELISA.
- Plasminogen Activator inhibitor (PAI-1): PAI-1 is secreted by thrombocytes during vessel regeneration. Patients with obesity and T2DM show higher basal values of PAI-1 which revealed to be related to a higher risk of atherothrombotic complications [17, 18]. Measurements of PAI-1 are performed by and ELISA method.

 endocrinology diabetology	Title: DIAPLATE-STUDY	Protocol No: Version 3.5	Sponsor: Medical University of Graz	Date: 13th February 2018
--	--------------------------	-----------------------------	--	-----------------------------

- Vascular adhesion molecule (VCAM): VCAMs are a group of cell adhesion molecules which promote adhesion of lymphocytes, monocytes and eosinophils to vascular endothelium. However it also may contribute to neointima formation after arterial injury and so on promotes vascular damage after acute vessel injury [19, 20]. Measurements are performed by an ELISA method.
- Intercellular adhesion molecule (ICAM): As VCAMs ICAMS are part of the immunoglobulin superfamily which take part in the leukocyte adhesion to endothelium and so contribute to augmentation of atherosclerotic plaque formation [21, 22]. Measurements will be performed by an ELISA method.

Counter regulatory hormones (CRH), C-peptide, renin, aldosterone, parathyroid hormone will be measured for a secondary objective to find out more about possible correlations with PAP and variations of counter regulatory hormones during the clamp, one day and one week after the trial.

- ACTH: Adrenocorticotropic hormone (ACTH) is measured in EDTA-plasma by an Immulite ® 2000 ACTH chemiluminescent immunometric assay (Siemens Healthcare Diagnostics Inc., Tarrytown, NY, U.S.A.)
- Cortisol: Serum Cortisol concentrations will be determined by the ADVIA Centaur cortisol assay which is a competitive immunoassay based on chemiluminescence technology assay (Siemens Healthcare Diagnostics Inc., Tarrytown, NY, U.S.A.)
- Aldosterone and Renin: They will be measured by the IDS-iSYS Aldosterone Renin assay which is based on chemiluminescence technology. (Immunodiagnosticssystems, Boldon, United Kingdom).
- C-Peptide: Serum C-peptide will be measured with the ADVIA Centaur which is a sandwich immunoassay (Siemens Healthcare Diagnostics Inc., Tarrytown, NY, U.S.A.)
- Epinephrine/ Norepinephrine: Normetanephrine and Metanephrine are measured in EDTA-plasma by a MetCombi Plasma ELISA (DRG Instruments GmbH, Marburg, Germany)
- IGF1: Insulin-like-growth factor1 (IGF1) will be measured with the IDS-iSYS assay which is based on chemiluminescence technology (Immunodiagnosticssystems, Boldon, United Kingdom)
- Glucagon will be analysed by using ELISA kits (Mercodia AB, Uppsala, Sweden)
- Parathyroid hormone (PTH): Intact PTH was determined in plasma by electrochemiluminescence immunoassay "ECLIA" on an Elecsys 2010 (ECLIA) (Roche Diagnostics, Mannheim, Germany)

6. ADVERSE EVENTS (AE)

An AE is any untoward medical occurrence in a patient or clinical trial subject administered a medicinal product and which does not necessarily have a causal relationship with this treatment. An AE can therefore be any unfavourable and unintended sign (including an abnormal laboratory finding), symptom, or disease temporarily associated with the use of the trial device/procedure, whether or not considered related to the treatment.

	Title: DIAPLATE-STUDY	Protocol No: Version 3.5	Sponsor: Medical University of Graz	Date: 13th February 2018
--	--------------------------	-----------------------------	--	-----------------------------

All adverse events that occur during this study will be recorded on the adverse event case report forms.

6.1. ADVERSE EVENT DESCRIPTION

For the purposes of the study, AEs will be followed up according to local practice until the event has stabilised or resolved, or the Follow-up Visit, whichever is the sooner. SAEs will be recorded throughout the study.

6.2. SEVERITY OF ADVERSE EVENTS

Mild: Awareness of event but easily tolerated

Moderate: Discomfort enough to cause some interference with usual activity

Severe: Inability to carry out usual activity

6.3. CAUSALITY OF ADVERSE EVENTS

Unrelated:	No evidence of any causal relationship
Unlikely:	There is little evidence to suggest there is a causal relationship (e.g. the event did not occur within a reasonable time after device implant). There is another reasonable explanation for the event (e.g. the patient's clinical condition, other concomitant treatment).
Possible:	There is some evidence to suggest a causal relationship (e.g. because the event occurs within a reasonable time after device implant). However, the influence of other factors may have contributed to the event (e.g. the patient's clinical condition, other concomitant treatments).
Probable:	There is evidence to suggest a causal relationship and the influence of other factors is unlikely
Definite:	There is clear evidence to suggest a causal relationship and other possible contributing factors can be ruled out

6.4. ABNORMAL LABORATORY TEST RESULTS

All clinically significant abnormal laboratory test results except increased fasting glucose and elevated HbA1c will be recorded as adverse events.

6.6. ADVERSE EVENTS RELATED TO THE CLAMP EXPERIMENT

The trial will include a hypoglycaemic clamp procedure during Visit 3. Within the clamp experiment hypoglycaemia is intentionally induced. Depending on potency of hypoglycaemia patients might feel discomfort, sweating, lack of concentration, dizziness, palpitations, or general discomfort. Hypoglycaemia will

	Title: DIAPLATE-STUDY	Protocol No: Version 3.5	Sponsor: Medical University of Graz	Date: 13th February 2018
--	--------------------------	-----------------------------	--	-----------------------------

be controlled by frequent venous glucose measurements. In case of unacceptable or unbearable hypoglycaemia during the clamp procedure, glucose will be administered and clamp investigation will be terminated if deemed necessary for the investigator or the subject wants to break up. During the entire clamp experiment, patients will be continuously monitored for glucose, heart rate, blood pressure and potassium. Medical staff is highly experienced and qualified for performing clamp investigations. The clamp may be interrupted or terminated for safety reasons at any time at the investigators discretion.

Independently from hypoglycaemia related adverse event, some discomfort may occur as a result from vein puncture or venous line issues. In some cases local haematoma can occur, very seldom installed venous lines might lead to local infection and phlebitis of the punctured vein which may require local and/or systemic treatment.

6.7. REPORTING OF SAEs

Rapid reporting of all SAEs, occurring during the study or within 30 days following the completion of the study by the subject, must be performed as detailed in SAE reporting instructions. SAE reporting instructions will be filed in the Investigator Site File. The sponsor will report the SAE to the ethics committee and local authorities.

A suspected unexpected serious adverse reaction (SUSAR) is designated as such according to Guideline 2001/20/EG. A serious adverse reaction is deemed unexpected when it is not listed in the corresponding basic document (Summary of Product Characteristics, IB, IMPD).

7. STATISTICAL ANALYSES

7.1 SAMPLE SIZE AND POWER CONSIDERATIONS

We have shown previously that light transmittance aggregometry (LTA) based on ADP activation in a population of subjects with type 2 diabetes is $70\pm12\%$ (Bethel MA et al. Diabetic Medicine 2016). For a clinically relevant difference in LTA from baseline to hypoglycaemia of 10% and assuming a standard deviation of 12%, 14 subjects are needed to achieve a power of 80% using a paired t-test with a 0.05 two-sided significance level. To account for potential study drop-outs, a maximum of 16 subjects will be included in this trial if required.

7.2 DATA ANALYSIS

The analysis of the collected data in the study will be performed with SAS v9.4. Demographic and baseline characteristics will be summarized descriptively. Continuous variables will be presented as means, standard deviation, median, minimum and maximum, for categorical data frequencies and relative frequencies will be used.

The primary endpoint changes in platelet activation measured by light transmittance aggregometry based on ADP activation from baseline to the end of the hypoglycaemia phase (i.e. 45 mg/dl for 30 minutes) at visit 3 will

	Title: DIAPLATE-STUDY	Protocol No: Version 3.5	Sponsor: Medical University of Graz	Date: 13th February 2018
--	--------------------------	-----------------------------	--	-----------------------------

be analysed using a paired t-test. Data will be adjusted for platelet activation variability captured at the euglycemic clamp visit. (Details will be outlined in the statistical analysis plan). A two-sided p-value of <0.05 is considered to indicate statistical significance.

The secondary endpoints will be presented descriptively and changes over the time points (from baseline to the end of the hypoglycaemia phase at visit 3) will be explored using parametric or non-parametric tests for dependent data. If applicable, linear models, accounting for the repeated measurements will be considered to investigate changes from the end of the hypoglycaemic clamp (last measurement of visit 3) to one day (visit 4) and 6±1 days after the clamp (visit 5) and changes during different states of hypoglycaemia at visit 3.

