10.1. Source Data	27
10.2 Language	28
10.3. Data Collection	28
10.6. Monitoring.....	28
11. DISCLOSURE OF DATA AND PUBLICATION	29
12. REFERENCES	31

	Title: DIAPLATE-STUDY	Protocol No: Version 3.5	Sponsor: Medical University of Graz	Date: 13th February 2018
--	--------------------------	-----------------------------	--	-----------------------------

Abbreviations

AE	Adverse event
ACTH	Adrenocorticotropic hormone
BMI	Body mass index
CRF	Case report form
CRH	Counter regulatory hormones
EC	Ethical Committee
ECG	Electrocardiography
FPPV	First patient first visit
FPLV	First patient last visit
GIR	Glucose infusion rate
HbA1c	Glycated haemoglobin 1c
HSS	Hypoglycaemic symptoms score
ICAM	Intercellular adhesion molecule
IGF-1	Insulin-like-growth factor 1
IL-6	Interleukin-6
PAI-1	Plasminogen activator inhibitor
PAP	Platelet activity parameters
PTH	Parathyroid hormone
PG	Plasma glucose
SDF	Source data form
T2DM	Type 2 Diabetes Mellitus
TMF	Trial master file
VCAM	Vascular adhesion molecule
vWF	von Willebrand factor

Sponsor	Medical University of Graz [name] 8036 Graz, Austria
Principal Investigators	[name], Associate Professor
Indication	Type 2 diabetes mellitus without history of cardiovascular disease
Study design and phase	Monocentric, single arm, open, mechanistic trial
Study Short Title	Platelet activity during hypoglycaemia
Keyword	Hypoglycaemia, platelet activity, type 2 diabetes mellitus
Aims of the trial	
Primary objective:
 
 - The primary objective is to investigate platelet activation during different levels of hypoglycaemia induced by a stepwise hyperinsulinaemic, hypoglycaemic clamp experiment in patients with T2DM 
Secondary objective:
 
To investigate
 
 - Platelet activation and recovery at one day and one week after the clamp experiment - Changes of proatherothrombotic markers during the hypoglycaemic clamp - Counter regulatory hormone response during the clamp

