Outcome measures of the trial	
Primary outcome measures:
 
 - Changes in platelet activation measured by light transmittance aggregometry based on ADP activation from baseline to the end of the hypoglycaemia phase (i.e. 45 mg/dl for 30 minutes) (visit 3) 
Secondary outcomes measures:
 
 - Changes in platelet activation measured by activation marker, such as CD62P, CD63 and PAC1, on CD41^{pos} or CD42b^{pos} platelets from baseline to the end of the hypoglycaemia phase - Changes in platelet activation measured by activation marker, such as LTA, CD62P, CD63 and PAC1, on CD41^{pos} or CD42b^{pos} platelets from the end of the hypoglycaemic clamp to one day after the clamp - Changes in platelet activation measured by activation marker, such as LTA, CD62P, CD63 and PAC1, on CD41^{pos} or CD42b^{pos} platelets from the end of the hypoglycaemic clamp to one week after the clamp - Changes in platelet activation measured by PFA-100 from baseline to the end of the hypoglycaemia phase - Changes in platelet activation measured by PFA-100 from the end of the hypoglycaemic clamp to one day and one week after the clamp - Changes in interleukin-6 (IL-6), von Willebrand factor [vWF], plasminogen activator inhibitor (PAI-1), vascular adhesion molecule (VCAM) and intercellular adhesion molecule (ICAM) from baseline to the end of the hypoglycaemia phase

	
 - Changes in interleukin-6 (IL-6), von Willebrand factor [vWF], plasminogen activator inhibitor (PAI-1), vascular adhesion molecule (VCAM) and intercellular adhesion molecule (ICAM) from the end of the hypoglycaemic clamp to one week after the clamp - Difference of platelet activation parameters during different states of hypoglycaemia - Counter regulatory hormone response during hypoglycaemia
Number of patients	
 - 14
Time schedule	
 - EC Submission: SEP/2017 - Local Authority Submission.: SEP/2017 - First Patient In (FPFV): JAN/2018 - Last Patient In: APR/2018 - Last Patient Out (LPLV): MAY/2018 - Data Base Lock: JUL/2018 - First Results available: JUL/2018 - Clinical Study Report: DEC/2018

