1. INTRODUCTION AND RATIONALE

Increased platelet activation is significantly involved in the pathophysiology of micro- and macrovascular diabetic complications. Previously performed studies suggested platelet activation in both, hyper- and hypoglycaemic states, leading to a potentially increased risk for thromboembolic complications. Hypoglycaemia, in particular severe hypoglycaemic episodes, has been associated with increased cardiovascular or overall mortality in previous studies [6, 7]. Potential mechanisms include arrhythmias or increased risk for thrombembolism, based on platelet activation and/or hypercoagulability.

However, studies investigating the effect of hypoglycaemia on platelet activity were mainly performed in healthy individuals or subjects with type 1 diabetes ([3],4,5]). In addition these studies did not systematically evaluate the correlation between the degree of hypoglycaemia and platelet activation in subjects with type 2 diabetes and the sustainability of platelet activation after the hypoglycaemic event.

Data on the impact of hypoglycaemia on platelet activation and markers of pro-atherothrombotic biomarkers in subjects with T2DM are scarce. Therefore we aim to explore platelet activation and atherothrombotic biomarkers during a stepwise hypoglycaemic clamp in subjects with T2DM and without established cardiovascular disease. In addition we aim to investigate for how long these potential effects sustain after the hypoglycaemic event.

Secondary objectives are to explore associations of the extent of hypoglycaemia and counter regulatory response and platelet activation.

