2.2 SECONDARY OBJECTIVES

To investigate

- Platelet activation and recovery at one week after the clamp experiment
- Changes of pro-atherothrombotic markers during the hypoglycaemic clamp
- Counter regulatory hormone response during the clamp

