2.4 SECONDARY OUTCOMES

- Changes in platelet activation measured by activation marker, such as CD62P, CD63 and PAC1, on CD41^{pos} or CD42b^{pos} platelets from baseline to the end of the hypoglycaemia phase
- Changes in platelet activation measured by activation marker, such as LTA, CD62P, CD63 and PAC1, on CD41^{pos} or CD42b^{pos} platelets from the end of the hypoglycaemic clamp to one day after the clamp
- Changes in platelet activation measured by activation marker, such as LTA, CD62P, CD63 and PAC1, on CD41^{pos} or CD42b^{pos} platelets from the end of the hypoglycaemic clamp to one week after the clamp
- Changes in platelet activation measured by PFA-100 from baseline to the end of the hypoglycaemia phase
- Changes in platelet activation measured by PFA-100 from the end of the hypoglycaemic clamp to one day and one week after the clamp
- Changes in interleukin-6 (IL-6), von Willebrand factor [vWF], plasminogen activator inhibitor (PAI-1), vascular adhesion molecule (VCAM) and intercellular adhesion molecule (ICAM) from baseline to the end of the hypoglycaemia phase
- Changes in interleukin-6 (IL-6), von Willebrand factor [vWF], plasminogen activator inhibitor (PAI-1), vascular adhesion molecule (VCAM) and intercellular adhesion molecule (ICAM) from the end of the hypoglycaemic clamp to one week after the clamp
- Difference of platelet activation parameters during different states of hypoglycaemia
- Counter regulatory hormone response during hypoglycaemia

	Title: DIAPLATE-STUDY	Protocol No: Version 3.5	Sponsor: Medical University of Graz	Date: 13th February 2018
--	--------------------------	-----------------------------	--	-----------------------------

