5.2.3. VISIT 3 – HYPERINSULINEMIC-HYPOGLYCEMIC CLAMP (10-24 DAYS AFTER VISIT 1)

[figure not shown]
The hyperinsulinemic-hypoglycemic clamp will be performed at Visit 3. Patients will be advised to attend to the study center (Clinical Research Center [CRC], [name], 8010 GRAZ) at 06:30 am after an overnight 10 hours fasting period. In case of antidiabetic treatment with Metformin, the morning dose should not be administered. Vital signs will be determined and documented, females with child bearing potential will do a pregnancy test and a physical status will be performed by the physician in charge, and possible Adverse Events will be documented. Patients will be advised to place in the study bed in which they will remain during the whole clamp experiment. Then, pulse and blood pressure monitoring will start.

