At approximately 07:00, two intravenous cannulas (catheters) will be inserted: one cannula will be inserted in an antecubital vein of a forearm for sampling of serial measurements of plasma glucose (approximately every 5-30 min, depending on the clamp procedure and safety). The hand will be placed in a heated environment to enable drawing of arterialised-venous blood. For controlled variable infusion of glucose 20% and infusion of human soluble insulin (40 IU Actrapid®, 100 IU/ml in 99.6 mL saline), an antecubital vein of the contralateral arm will be cannulated. Both cannulas will be kept open by a slow continuous 0.9% saline infusion. After the baseline blood samples for blood glucose, insulin, counter regulatory hormone parameters and platelet activity have been taken, the hyperinsulinemic hypoglycemic clamp will be started. A variable i.v. infusion of glucose 20% or infusion of human soluble insulin will be initiated in order to obtain a plasma glucose target of 5.5 mmol/L (100 mg/dL) \pm 10%. When the plasma glucose target of 5.5 mmol/L (100mg/dL) \pm 10% is reached the high constant insulin infusion (2.5 mU/kg/min) will be initiated. After 30 minutes the plateau 5.5mmol/L will be started. After 30 min on the 5.5 mmol/L plateau the glucose infusion will be interrupted, the PG will be allowed to decline to 3.5 mmol/L and by restarting the variable glucose infusion, kept stable at 3.5 mmol/L. Thereafter the glucose infusion will be interrupted and the PG will be allowed to decline to 2.5 mmol/L or a nadir at a higher concentration in case 2.5 mmol/L cannot be reached or symptoms of hypoglycaemia are unacceptable. By restarting the variable glucose infusion the PG will be kept stable at 2.5 mmol/L or nadir and assessments on the plateau will be performed. After 15 min on the 2.5 mmol/L or nadir plateau the constant high insulin infusion will be terminated. Starting at time point 25 min on the 2.5 mmol/L or nadir plateau the glucose infusion will be tapered off, if possible, to allow a spontaneous recovery from hypoglycaemia. PG will not be allowed to fall below 2.2 mmol/L. If PG has not reached 4.0 mmol/L 45 min after termination of the constant high insulin infusion, a constant high glucose infusion (5.5 mg/kg/min) will be initiated to increase PG to a level of 4.0 mmol/L. When reaching the PG level of 4.0 mmol/L assessments will be performed and blood samples will be taken. The PG will then be increased to 5.5 mmol/L for safety reasons and the clamp terminated, if deemed safe by the investigator. PAP and CRH samples will be obtained at the end of each plateau phase as well as after recovery from hypoglycaemia at PG 100mg/dl (see figure 1).

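### The named follow-up contrast for platelet markers starts from the post-recovery sample at Visit 3, so by itself it cannot tell sustained activation from activation that had already resolved

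*Combined protocol and SAP*

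**What the plan says.** **The question.** Section 1 states: "In addition we aim to investigate for how long these potential effects sustain after the hypoglycaemic event". The synopsis lists as a secondary objective "Platelet activation and recovery at one day and one week after the clamp experiment"; Section 2.2 has the one-week part only: "Platelet activation and recovery at one week after the clamp experiment".

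**The contrasts.** In the synopsis, Section 2.3, Section 2.4 and Section 7.2, every contrast named from baseline stops at the end of the hypoglycaemia phase within Visit 3. Every follow-up contrast starts later. For aggregometry and the flow markers it runs "from the end of the hypoglycaemic clamp to one day after the clamp", with a parallel item for one week. For the platelet function analyser it is "Changes in platelet activation measured by PFA-100 from the end of the hypoglycaemic clamp to one day and one week after the clamp". The soluble markers (IL-6, vWF, PAI-1, VCAM, ICAM) have a one-week item with the same start. Section 7.2 fixes that start by proposing models to "investigate changes from the end of the hypoglycaemic clamp (last measurement of visit 3) to one day (visit 4" and to Visit 5.

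**The samples.** Section 5.2.3 (Visit 3) provides for a platelet sample before the clamp and then says: "PAP and CRH samples will be obtained at the end of each plateau phase as well as after recovery from hypoglycaemia at PG 100mg/dl". Section 5.3.7 gives five platelet time points per clamp and further platelet samples at Visits 4 and 5.

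**The rest of the plan.** Section 7.2 also promises descriptive presentation of the secondary endpoints, and says that repeated-measures models will be considered where applicable. It refers to a separate statistical analysis plan directly after the adjustment of the primary endpoint; that plan is not in the supplied text.

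**The concern.** Whether an effect lasts, or has recovered, is a question about the level before hypoglycaemia. A contrast that starts from a sample taken after glucose has been restored measures only what happens from then on. If activation had already faded by that sample, no further change is expected. If activation was still fully present and stayed so for a day, no further change is expected either. The same null result fits opposite answers.

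At stake is the interpretation of a stated secondary aim. The trial could report no change from the end of the clamp to Visit 4 or Visit 5 without a planned interval saying how far patients were from where they started, although the samples needed for it are collected.

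**Working it through.** **1. The plan's own figure.** Section 7.1 assumes a 10-point difference in ADP aggregation, SD 12, a paired t-test, two-sided 0.05 and 80% power. The exact noncentral t calculation gives 78.8% power at n = 13 and 82.2% at n = 14, so 14 subjects is reproduced. The sample size is not in dispute.

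**2. Which sample is the reference.** Section 7.2 equates the end of the clamp with the last Visit 3 measurement. Section 5.2.3 (Visit 3) puts the last platelet sample after recovery at 100 mg/dl. The five time points in Section 5.3.7 fit: pre-clamp, the 5.5, 3.5 and 2.5 mmol/L (or nadir) plateaus, and recovery. Section 2.4 also treats the end of the hypoglycaemia phase and the end of the clamp as different moments. Figure 1 is not shown, so this rests on the text. Section 5.2.3 also mentions blood samples at 4.0 mmol/L without naming the analytes, but that step precedes the return to 5.5 mmol/L. For the soluble markers the text gives no last Visit 3 sampling time, so the argument is confined to platelet markers.

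**3. What the contrasts return.** The mean profiles are assumed; the 70 and the 10-point rise follow Section 7.1. Rejection rates come from 20,000 simulated trials with n = 14, paired t-tests and SD 12 for every paired difference.

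| Profile | Baseline / hypoglycaemia / last V3 / V4 | V4 − last V3 (rejected) | V4 − baseline (rejected) |
|---|---|---|---|
| Sustained | 70/80/80/80 | 0 (5.1%) | +10 (82.2%) |
| Resolved within the clamp | 70/80/70/70 | 0 (5.2%) | 0 (5.0%) |
| Half resolved, then sustained | 70/80/75/75 | 0 (5.1%) | +5 (30.4%) |
| Resolved after the clamp | 70/80/80/70 | −10 (82.0%) | 0 (5.1%) |

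The named contrast is identical in the first three rows. It is informative in the fourth, so it is worth keeping.

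**4. Precision of the added contrast.** Half-width = t(0.975, 13 df) × SD / √14, with t = 2.160. The documents give no SD for change to Visit 4 or 5. If 12 were the SD of a single sample, the SD of change would be 12 × √(2(1 − r)): about 8 at r = 0.78, 12 at r = 0.5 and 17 at r = 0.

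- SD 8: 2.160 × 8 / √14 = 4.6. An observed +10 gives 5.4 to 14.6; an observed 0 gives −4.6 to 4.6.
- SD 12: 2.160 × 12 / √14 = 6.9. An observed +10 gives 3.1 to 16.9; an observed 0 gives −6.9 to 6.9.
- SD 17: 2.160 × 17 / √14 = 9.8. An observed +10 gives 0.2 to 19.8; an observed 0 gives −9.8 to 9.8.

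**5. Number of added contrasts.** Section 5.3.7 lists four aggregation agonists, two analyser cartridges and three flow markers. With flow markers on platelets only: (4 + 2 + 3) × 2 visits + 5 soluble markers at Visit 5 = 23. If the flow markers on platelet-leukocyte complexes are included: (4 + 2 + 6) × 2 + 5 = 29. With ADP as the only agonist: (1 + 2 + 3) × 2 + 5 = 17, or (1 + 2 + 6) × 2 + 5 = 23. If nothing truly changed, the full sets would give about 23 × 0.05 = 1.2 to 29 × 0.05 = 1.5 unadjusted intervals excluding zero.

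**The case against.** The strongest reply is that the plan already covers most of this. Means by visit would distinguish 70/80/80/80 from 70/80/70/70 at a glance. If the pre-clamp sample is included in the repeated-measures model, Visit 4 minus baseline is one further contrast statement. A comparison of the last Visit 3 sample with baseline would also separate the two cases. The study is small and mechanistic, these analyses are exploratory, and the unseen analysis plan may contain the contrast.

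Much of that stands, which is why the point is limited to what the named contrast can do by itself. What remains is that a table of means gives no interval for a within-patient change, and that Section 7.2 only considers the model and names other comparisons for it.

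A second objection also stands: the added contrast has limits of its own. The design is single-arm, and Table 1 has no next-day or one-week visit after the euglycaemic clamp. A rise over baseline at Visit 4 could come from insulin, the procedure or day-to-day variation as well as from hypoglycaemia. Nor are the samples fully matched. Visit 3 baseline blood is drawn "after an overnight 10 hours fasting period" through a line set up for arterialised-venous sampling, while Visit 4 blood is described as venous. The statement that follow-up samples are fasting appears under routine biochemistry (Section 5.3.5), so applying it to platelet samples is an inference.

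**Conclusion.** The point holds for the supplied text. The protocol asks how long platelet activation lasts, and its named follow-up contrast for platelet markers returns the same value, zero, whether activation is fully sustained, half resolved or fully resolved by the last Visit 3 sample. The direct contrast from baseline separates these cases (+10, +5 and 0 in the illustration). This is worth correcting, but it concerns a secondary, exploratory aim and leaves the primary analysis alone.

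The conclusion assumes that the post-recovery sample is the last platelet sample of Visit 3, as the text indicates without Figure 1. The half-widths of 4.6 to 9.8 points rest on assumed SDs.

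Three stronger readings are not supported:

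- A reader might infer that the planned follow-up contrast is useless. It is not: it detects recovery that occurs after the clamp.
- A reader might infer that the analysis plan omits the baseline contrast, or that it will be picked after the data are seen. The content of that plan is not available, so neither can be said.
- A reader might infer that a difference from baseline at Visit 4 or 5 would demonstrate a lasting effect of hypoglycaemia. Without follow-up after the euglycaemic clamp it shows persistence only.

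**What to change.** In Sections 2.4 and 7.2, or in the statistical analysis plan before the data are examined:

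- Add, as exploratory paired or repeated-measures estimates with 95% confidence intervals, the change from the Visit 3 pre-clamp baseline to Visit 4 and to Visit 5 for the platelet markers, with ADP aggregometry listed first, and to Visit 5 for the soluble markers.
- Keep the end-of-clamp contrasts, and name the reference sample of each contrast, including the last Visit 3 sampling time of the soluble markers.
- State that a non-significant difference from baseline is not read as recovery.
- State that, in a single-arm design without follow-up after the euglycaemic clamp, a difference from baseline cannot be attributed to hypoglycaemia alone.
- Note that baseline blood is arterialised-venous and Visit 4 blood venous.

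The cost is a few sentences, with no new samples or visits. The downside is more exploratory intervals, wide at 14 subjects: 23 or 29 depending on whether platelet-leukocyte complexes are included, with about one or two likely to exclude zero by chance. Restricting aggregometry to ADP lowers the count to 17 or 23.
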